The null hypothesis is that the mean maximum eosinophils count in the active treatment group is the same as that in the placebo treatment group. This hypothesis will be evaluated using an analysis of covariance (ANCOVA) model with treatment group, baseline patient's maximum esophageal eosinophil count, and age group (4-11 years old versus 12-17 years old) as covariates. The primary comparison will be tested at the 5% significance level. The least square means for the treatment groups, difference in least square means between the treatment groups, effect size calculated as the absolute difference in least square means between active group and placebo divided by the root mean square, and p-value for difference between treatment groups will be presented.

Secondary Efficacy Analyses

The mean Esophageal Eosinophil Count of the all specimens obtained at the end of treatment and end of the open label extension and percentage of subjects with less than 15 eosinophils/HPF at the end of treatment will be summarized descriptively by treatment group. Changes in individual and total symptoms scores will be summarized descriptively

by treatment group. For the upper endoscopies, visual score at baseline and at the end of treatment at double blind and open label extension will be summarized. Comparisons between groups using a Student's t-test or a Mann-Whitney test for continuous variables and a chi-square tests for categorical variables will be presented.

VERSION AND DATE: 8.0 (Amendment 7), 21 August 2017

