11.9 Histological Evaluation

Prior to randomization, esophageal biopsy samples will be evaluated to confirm eligibility. Biopsy samples will be stained with hematoxylin and eosin stain. Intraepithelial eosinophils will be counted in all HPFs using 400X light microscopy. A HPF will be counted only if at least half of the field is occupied by tissue. The maximum eosinophil count per HPF will be reported for each esophageal biopsy site (at each of 2 levels). In addition to the evaluation for eosinophilia, all biopsy samples will be assessed for other histologic changes including epithelial hyperplasia, intercellular edema, and fibrosis. Histologic evaluation to be completed by a blinded Pathologist at CHOP.

At the end of each treatment period (Visit 10 and Visit 16), the esophageal biopsy specimens from all subjects will be evaluated in a blinded fashion by an independent pathologist. Specimens will be examined with respect to the maximum eosinophil counts and other histologic changes. Together with the EoE Clinical Symptom Score, the maximum eosinophil count per HPF for each specimen (from the total of all specimens) will be used to determine response to treatment.

The maximum eosinophil count will be defined as the highest number of eosinophils observed in any single HPF from an esophageal specimen. All specimens from all esophageal sites will be considered in determining the resolution of eosinophilia. A maximum eosinophil count will be recorded for the esophagus. The highest peak counts at a given timepoint (screening or end of each treatment visit) will be referred to as the maximum eosinophil count for that timepoint. The

mean Esophageal Eosinophil count will be the mean score of each of the high power fields from the all biopsy specimens.

As a confirmatory marker of EoE disease activity, we will use paraffin-embedded esophageal biopsies already obtained for routine clinical care to identify innate immune cell populations as well as chemokine expression through immunohistochemistry staining.

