13.2 Sample Size Estimation

This is a pilot study in which we aim to identify efficacy of the Viaskin® Milk treatment. Sample size is based on projected subject volume. If efficacy is shown, our pilot data could be used to perform a power analysis for a larger study.

We will recruit 38 subjects and plan to have approximately 22 evaluable subjects with milk-induced EoE confirmed by endoscopy and biopsy.

A total sample size of 22 evaluable subjects (16 subjects in the active Viaskin® Milk group and 6 subjects in the placebo group) will achieve 90% power to detect a difference of 40 in mean maximum eosinophil counts between the two treatment groups (mean maximum eosinophil counts of 10 and 50 in Viaskin® Milk and in placebo, respectively) assuming that a common standard deviation is 20 using a two group *t*-test with a two-sided significance level of 0.05.

Approximately 22 subjects will be randomized to obtain 18 completed subjects with 10% drop-out.

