In addition, the change from baseline to end of treatment of the total symptom score and individual symptom scores (Abdominal/chest pain score, Vomiting score, and Dysphagia score) will be generated by treatment group and overall. The comparison of the change of individual symptom scores between the two treatment groups will be evaluated by using Fisher's exact tests.

The responses will be divided into three categories as suggested: Poor <30% improvement, good 30-70% improvement and excellent >70% improvement from baseline.

Percentage of subjects per response rate

The percentage of subjects showing an excellent response (≤ 1 eos/HPF), good response (2-14 eos/HPF), or poor response (≥ 15 eos/HPF) at the end of treatment will also be presented and analyzed between the two treatment groups using Fisher's exact test.

Eosinophilic Esophagitis Quality of Life Score

The Quality of Life score will also be reported for each treatment group at baseline and the end of treatment. The change from baseline to end of treatment will also be presented. The change in QOL scores between two treatment groups will be compared with two-sample t-test or Mann-Whitney test depending on the distribution of the change of the QOL score.

Combination Score:

Combination Score of four measures (Eosinophils/HPF, EREFS, investigator assessment and parental assessment of symptoms) will be calculated at baseline, end of treatment and end of study. The combination score will be calculated as (maximum eosinophils per high power field) + [10*esophageal endoscopy score (EREFs)] + [2* Parent assessment of esophageal symptoms (PEESS)] + [5*investigator assessment of EoE symptom activity]. The change from baseline to end of treatment will also be presented. The change in QOL scores between two treatment groups will be compared with two-sample t-test or Mann-Whitney test depending on the distribution of the change of the QOL score.

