#### **4.4.2.3 Percentage of subjects per response rate**

The percentage of subjects showing an excellent response ( $\leq 1$  eosinophils/HPF), good response (2-14 eosinophils/HPF), and poor response ( $\geq 15$  eosinophils/HPF) at the end of the double-blind treatment and at the end of the open-label treatment as well as RR (i.e., the percentage of subjects showing excellent response in the treatment group divided by the percentage of subjects showing excellent response in the placebo group) along with 95% CIs between two treatment groups will be presented (*Table 13*).

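### The Visit 10 histologic bands are the same throughout, but the comparison made on them is not fixed; one exact 2x2 comparison at <15/HPF would serve better than an unordered three-band test or a relative risk for each band

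*Protocol*

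**What the plan says.** The categories never change: ≤1, 2-14 and ≥15 eosinophils/HPF in the synopsis, Protocol 8.6.1.2 and 13.6.4.2, and SAP 2.2.4 and 4.4.2.3. What is done with them does change.

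- **Protocol synopsis, Secondary Efficacy Analyses:** the "percentage of subjects with less than 15 eosinophils/HPF at the end of treatment" is summarised by arm, and chi-square is the test named for categorical variables.
- **Protocol 13.6.4.2:** "The percentage of subjects showing an excellent response (≤ 1 eos/HPF), good response (2-14 eos/HPF), or poor response (≥ 15 eos/HPF" is presented at end of treatment and compared between arms by Fisher's exact test on the three bands.
- **SAP 4.4.2.3:** no test is named. A relative risk with 95% CI is planned, explained as "the percentage of subjects showing excellent response in the treatment group divided by the percentage of subjects showing excellent response in the placebo group". The Table 13A shell has one relative-risk column running across all three bands.
- **Protocol 11.9:** "Together with the EoE Clinical Symptom Score, the maximum eosinophil count per HPF for each specimen" is to be used to determine response to treatment. No cut-off, combining rule, test or table follows.

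**The concern.** With about 22 children, chi-square at <15, Fisher on three bands and a relative risk for excellent response can point in different directions, and nothing says which one is the response result. Two of the choices are also weak in themselves.

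The bands are ordered, but a Fisher test on a 2x3 table treats them as labels and spends power on patterns nobody expects. The middle band is not a measure of benefit: a better drug moves children out of poor into good, but also out of good into excellent, so the 2-14 share can go either way.

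The 15/HPF cut is the plan's own dividing line. It defines active disease at entry, separates poor from the other bands, and sorts children by diet in the open-label period. It is the natural place to make a single comparison.

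**Working it through.** **Inputs (Protocol 13.2).** "mean maximum eosinophil counts of 10 and 50 in Viaskin® Milk and in placebo, respectively"; "assuming that a common standard deviation is 20"; "with a two-sided significance level of 0.05"; "16 subjects in the active Viaskin® Milk group and 6 subjects in the placebo group) will achieve 90% power". The same section expects 18 completers without giving their split, so 14:4 and 13:5 are both shown as assumptions. No response rates are given; they are derived below under three assumed distributions.

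**The plan's own figure.** The noncentrality is 40/(20·√(1/16+1/6)) = 4.18 on 20 df, which gives t-test power of 97.8%, not 90%. At 14:4 it is 3.53 on 16 df, giving 91.1%. So the stated 90% fits 18 completers rather than 22. It concerns the primary endpoint; no power is stated for the bands.

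**Band probabilities.** Each model has means 10 and 50 and SD 20.

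- Normal, cuts at 1.5 and 14.5: P(<15) = Φ((14.5−10)/20) = 58.9% active and Φ((14.5−50)/20) = 3.8% placebo. P(≤1) = 33.5% and 0.8%. The 2-14 band is the difference, 25.4% and 3.0%. This model puts Φ(−0.5) = 31% of the active arm below zero.
- Negative binomial, size = mean²/(SD²−mean): <15 is 79.8% and 1.0%; ≤1 is 48.5% and about 0%.
- Lognormal, log-variance = ln(1+SD²/mean²), same cuts as the normal: <15 is 82.3% and 0.1%; ≤1 is 19.5% and about 0%.

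**Power, by full enumeration.** Fisher's exact test for 2x2; Fisher-Freeman-Halton for 2x3. Losses are taken from unrounded figures.

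| Model | Split | 2x2 at <15 | Three bands | Loss (points) |
|---|---|---|---|---|
| Normal | 16:6 | 57.0% | 41.7% | 15.3 |
| Normal | 14:4 | 22.0% | 14.8% | 7.2 |
| Normal | 13:5 | 47.1% | 27.7% | 19.4 |
| Negative binomial | 16:6 | 98.1% | 96.0% | 2.0 |
| Negative binomial | 14:4 | 84.9% | 74.8% | 10.1 |
| Negative binomial | 13:5 | 95.7% | 87.8% | 7.9 |
| Lognormal | 16:6 | 99.6% | 98.5% | 1.1 |
| Lognormal | 14:4 | 91.3% | 83.0% | 8.2 |
| Lognormal | 13:5 | 98.2% | 93.8% | 4.4 |

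The 2x2 test is ahead in every row. At the 15:5 split in SAP 3.2, the normal-model pair is 48.7% and 26.0%. Ignoring the order is what costs power: an exact Wilcoxon-type test on the same three bands gives 59.4% at 16:6 under the normal model.

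**The 2-14 band.** Under the negative binomial with SD 20, lowering the active mean from 15 to 10 to 5 takes <15 from 66% to 80% to 92%, while 2-14 goes from 43% to 31% to 11%. Under the normal model 2-14 stays near 25% throughout.

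**The excellent relative risk.** The chance that none of six placebo children is ≤1/HPF is (1−0.0077)⁶ = 95.5% under the normal model, and practically 100% under the other two. The ratio then has a zero denominator. With 0.5 added to the cells, the 95% CI almost never excludes 1. A Fisher test does little better at 16:6: with no placebo responder it needs 9 of 16 active responders (p = 0.046; 8 of 16 gives 0.051), and its power at ≤1 is 5.0%, 35.7% and 0.1% under the normal, negative binomial and lognormal models.

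**The case against.** The strongest reply is that the contrast at 15 is already planned. Poor (≥15) is the exact complement of <15, is a listed endpoint, and has its own row under the relative-risk column of Table 13A. The excellent ratio in SAP 4.4.2.3 can be read as showing how a relative risk is formed, not as choosing the contrast. That stands. The poor-row ratio is also nearly always computable, so the fix promotes something already in the shell. It does not settle which row or method is the response result, and it does not rescue the other two rows.

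It is also fair that these are secondary analyses in a pilot, with no power claimed, and that the SAP leans on estimates and intervals rather than tests. A reader who sees all three bands side by side can follow children moving from good to excellent.

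Two stronger readings are tempting. A reader might infer four competing definitions of response. The documents do not support that: <15 and ≤1 are collapses of the same three bands, and the sentence in Protocol 11.9 has no rule on which anything could be compared. It may simply name two outcome domains, since 13.6.4.2 has a separate symptom-responder rule.

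A reader might also infer that the choice moves power from 57% to 5%. Those are Fisher powers at <15 and ≤1, at 16:6, under the normal model with its 31% negative counts. No section assigns Fisher's test to either contrast alone. The synopsis pairs chi-square with <15, which gives 79% under the same model, and the SAP plans only a ratio with a CI. The fall from <15 to ≤1 is large in every model tried, but that pair of figures is not the power of the planned analyses.

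**Conclusion.** The concern holds in a limited form. The bands agree across the documents; the contrast and method applied to them do not, and nothing says which governs. A 2x2 Fisher test at <15/HPF has more power than the unordered three-band test in every distribution and split tried. The gain at 16:6 is about 15 points under normality and 1 to 2 points under the two non-negative models. At 18 completers it is about 4 to 19 points. These figures rest on the planning means and SD, on distributions the plan does not specify, and on an assumed split of completers, so they should be read only as a range.

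Two further points do not depend on power. A relative risk for 2-14 alone is not a measure of benefit, though how far it misleads depends on the distribution. The excellent relative risk will usually be incalculable, and the SAP gives no rule for a zero cell. The change is minor and does not touch the primary analysis of the maximum count.

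**What to change.** - In Protocol 13.6.4.2 and SAP 4.4.2.3, name maximum count <15/HPF at Visit 10 (the complement of the existing poor row) as the response comparison, with a 2x2 exact test. Align the synopsis, replacing chi-square there: under the normal model the expected placebo responder cell is (16×0.589 + 6×0.038)×6/22 ≈ 2.6, small for a large-sample test.
- Give ≤1/HPF as a supportive cumulative cut, with an estimate that survives a zero cell, such as an exact CI for the risk difference.
- Keep the three bands in Table 13A as counts and percentages, with no relative risk for 2-14.
- Reconcile the sentence in Protocol 11.9 on count together with symptoms: either give the rule, or say that histologic and symptom response are assessed separately.
- If power is quoted for any of these, give a range and state the distribution assumed.

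The cost is wording in the two documents and one table shell. No new data are needed.

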13.6.5 Pharmacokinetics

Not applicable, no pharmacokinetic assessments will be performed during this study.

13.6.6 Safety

No formal statistical analysis of safety endpoints will be carried out.

13.6.6.1 Adverse Events

All AEs will be coded by system organ class and preferred term using MedDRA. Treatment-emergent AEs (TEAEs) will be defined as any AEs, regardless of relationship to study drug, which occur during AE collection period of study drug or any event already present that worsens in either intensity or relationship to study drug following exposure to the Viaskin®. If relationship information is missing, the TEAE will be considered drug-related.

An overall summary of TEAEs will be provided showing the number and percentage of subjects in each treatment group with any TEAE, any potentially drug-related TEAE, any severe TEAE, any serious TEAE, any TEAE leading to discontinuation, and any TEAE leading to death. The number of events will also be presented.

The number of AEs as well as the number and percentage of subjects who experienced at least one AE will be summarized by system organ class, preferred term and treatment group. The incidence of the following events will be summarized:

- Local skin tolerance: incidence, severity and duration of local TEAE at site of Viaskin® application as reported by subjects in the diary card
- TEAEs: incidence, severity and duration.
- Potentially drug-related TEAEs
- Discontinuations due to TEAEs
- Laboratory data, physical examinations, and vital signs Systemic allergic symptoms in the active and placebo groups
- Potentially drug-related systemic allergic symptoms
- SAEs
- Potentially drug-related SAEs

In addition, TEAEs will be summarized by relationship to study drug and by severity. If a subject has more than one occurrence of the same TEAE with different severities or relationship to study drug, then the TEAE will be assigned to the highest severity category and/or most related relationship category. If the intensity or relationship is missing, then the 'worst case' will be assumed (i.e., severe for intensity and drug-related for relationship).

The proportion of subjects that experience systemic allergic symptoms will be summarized by treatment. All TEAEs will be listed.

13.6.6.2 Laboratory Assessments

Descriptive statistics will be calculated for clinical laboratory tests (hematology and biochemistry) performed at baseline (Day 1), Visit 10 (end of DBPC treatment) and visit 16 (end of open label extension). Categorical variables will be summarized by frequency and percentages of subjects in corresponding categories. Changes from baseline will also be presented.

In addition, summaries of laboratory values categorized based on CTC (common toxicity criteria) grade will also be presented.

All laboratory data will be listed. Listing of values that are out of normal range will be flagged in the data listings.

13.6.6.3 Vital Signs

Observed vital sign values and changes from baseline will be descriptively summarized by visit and treatment group. All vital signs data will be listed.

The analysis of vital signs will focus on the incidence of clinically relevant abnormalities. The number of subjects evaluated and the number and percentage of subjects with clinically relevant post-baseline abnormalities at each visit will be presented.

Table 6 Criteria to Determine Clinically Relevant Abnormalities in Vital Signs - Children

Vital Sign	Criteria for Abnormalities
Temperature	<35°C and a decrease from pre-dosing of at least 1°C > 38.5°C and an increase from pre-dosing of at least 1°C
Pulse	> 120 beats per minute or an increase from pre-dosing of > 20 beats per minute, or < 50 beats per minute or a decrease from pre-dosing of > 20 beats per minute
Systolic blood pressure	> 140 mmHg or an increase from pre-dosing of > 40 mmHg, or < 90 mmHg or a decrease from pre-dosing of > 30 mmHg
Diastolic blood pressure	> 90 mmHg or an increase from pre-dosing of > 30 mmHg, or < 50 mmHg or a decrease from pre-dosing of > 20 mmHg

13.6.6.4 Concomitant Medications

Concomitant medications will be coded using the WHO Drug Dictionary. A summary of concomitant medications will be produced by preferred drug name and treatment group. All concomitant medications will be listed.

13.6.7 Additional Data

Diary card data, Viaskin® site examination and physical examination data will be summarized where appropriate and listed. Study drug compliance and accountability will be listed.

13.6.8 Data and Safety Monitoring Board

A DSMB will be composed to review the safety and/or efficacy data of the study at any time judged necessary during the course of the study and after the first 3 patients are enrolled and then annually. Members of the DSMB will be selected and confirmed as early as possible, in any case before the first data review is convened. Ideally, the DSMB should be composed of experts in food allergy and in the methodology of clinical trials. The DSMB will review either blinded or unblinded data during the course of the study (see below). Various recommendations will then be made by the DSMB. The three members of the DSMB are [name], Chief of Allergy and Immunology, Arkansas Children's Hospital, Univ. of Arkansas School of Medicine; [name], PhD, Director of Eosinophilic Esophagitis Center, Rady's Children's Hospital, University of California at San Diego; and [name], Univ. of Colorado School of Medicine. Westat will supply blinded study results to the DSMB unless unblinded results are requested by the DSMB for safety reasons. For details of the emergency procedure for unblinding of individual subjects, see Section 8.5.10

14. MONITORING PROCEDURES (QUALITY ASSURANCE)

The Principal Investigator has ethical, legal, and scientific obligations to conduct this study in accordance with established research principles and ICH GCP guidelines. As such, in order to fulfill these obligations and to maintain current of study progress, the Investigator's monitors or representatives will visit the investigative site during study conduct, in addition to maintaining telephone and written communication. On-site visits, telephone calls, and regular inspection of the eCRFs will be conducted in order to assess subject enrollment, compliance with protocol procedures, completeness and accuracy of data entered on the eCRFs, verification of eCRF data against original source documents, and occurrence of AEs. The Investigator must provide the monitor with full access to all source and study documents.

14.1 Routine Monitoring

Investigator assigned monitors will conduct regular site visits at the one clinical site (CHOP) for the purpose of monitoring various aspects of the study. The monitor will access to the clinical (or associated) files and clinical study supplies (dispensing and storage areas) for all study subjects considered for study entry for the purpose of verifying entries made in the eCRF, and assist with their activities, if requested. Adequate time and space for monitoring visits should be made available by the Investigator.

CHOP staff must complete the eCRFs in a timely manner and on an ongoing basis to allow regular review by the study monitor.

See Appendix 3 for monitoring plan.

14.2 Inspections and Auditing Procedures

The Investigator monitor may conduct audits at the investigative sites including, but not limited to, drug supply, presence of required documents, the informed consent process, and comparison of eCRFs with source documents. All medical records (progress notes) must be available for audit. The Investigator agrees to participate with audits conducted at a convenient time in a reasonable manner.

Government regulatory authorities may also inspect the Investigator during or after the study. The Investigator or designee should contact the Sponsor /CRO immediately if this occurs. He/she must cooperate fully with regulatory authorities or other audits conducted at a convenient time in a reasonable manner.

The purpose of an audit is to assess whether ethics, regulatory and quality requirements are fulfilled.

